APPENDIX C. PROTOCOL AMENDMENT SUMMARY OF CHANGES

Document	Date
Amendment 1	30 NOV 2022

Amendment 1 (30 NOV 2022)

Overall Rationale for the Amendment

The primary purpose of this amendment is to clarify that Day 1 serum chemistry and hematology testing will be performed only if the screening laboratory test date is more than 2 weeks before Day 1. Additional changes and clarifications are summarized below.

1. Section 1, Protocol Summary (Table 3: Schedule of Activities: Continuous Treatment Period; Table 4: Schedule of Activities: Long-Term Safety Period); Section 6.1.1, Study Treatment Application Guidance; Section 8.4, Pharmacokinetic Assessments (Table 10: Pharmacokinetic Blood and Saliva Sample Timing)

Description of change: Removed the requirement for all morning study cream applications to be performed at the site, and revised to allow participants to apply either of the 2 daily doses at the site after Day 1.

Rationale for change: To allow flexibility in appointment time and to ease the burden on the participant and/or legal guardian.

2. Section 1, Protocol Summary (Table 3: Schedule of Activities: Continuous Treatment Period); Section 8.3.5, Laboratory Assessments

Description of change: Updated to clarify that Day 1 testing for serum chemistries and hematology will only be performed if the interval between Day 1 and the date of the screening laboratory tests is great than 2 weeks.

Rationale for change: To clarify when Day 1 testing is required.

3. Section 1, Protocol Summary (Table 3: Schedule of Activities: Continuous Treatment Period; Table 4: Schedule of Activities: Long-Term Safety Period)

Description of change: Added an assessment for Itch NRS eDiary compliance.

Rationale for change: To improve compliance of Itch NRS eDiary assessments.

4. Section 1, Protocol Summary (Table 3: Schedule of Activities: Continuous Treatment Period); Section 8.4, Pharmacokinetic Assessments (Table 10: Pharmacokinetic Blood and Saliva Sample Timing)

Description of change: Revised the timing of the PK blood draw from morning to any time prior to study drug application but at least 4 hours after the previous application of study cream. Also, provided guidance on blood draws from treated areas if no other acceptable blood draw areas are available.

Rationale for change: To decrease participant burden by allowing flexibility in the appointment time and minimize missed PK assessments.

5. Section 3, Objectives and Endpoints (Table 5: Objectives and Endpoints)

Description of change: Revised the exploratory endpoints for the evaluation of efficacy of ruxolitinib cream in adolescents with AD. Removed the Itch NRS score at each postbaseline visit, and add measurement timing for EASI scores, itch scores, and ITCH4.

Rationale for change: To include the analysis of EASI scores and also the daily itch and Itch NRS responses at each postbaseline visit.

6. Section 5.2, Exclusion Criteria (Criterion 12)

Description of change: Deleted the exclusion criterion regarding the inability to draw blood for PK from any nonlesional areas.

Rationale for change: To allow for drawing blood from a treated area provided the study cream is not applied at that area during the previous application.

7. Section 6.2, Preparation, Handling, and Accountability

Description of change: Revised study cream accountability at the conclusion of the study to reflect the process for handling remaining study cream for destruction at the site, or if local procedures do not allow on-site destruction, then shipment back to the sponsor is allowed.

Rationale for change: To reflect the current procedure for sample accountability following completion of the study.

8. Section 6.6, Concomitant Medications and Procedures

Description of change: Clarified the timeframes to be followed for recording in the eCRF for non-AD medications and treatments and for AD medications and treatments.

Rationale for change: To allow collection of prior AD medications and treatments for a 12-month period.

9. Section 6.6.2, Restricted Medications and Procedures; Section 6.6.3, Prohibited Medications and Procedures

Description of change: Updated to allow the short-term use of systemic corticosteroids to treat acute AEs (eg, asthma) during the LTS period.

Rationale for change: To allow for short-term treatment of a concomitant illness which has no impact on safety or efficacy.

10. Section 8.1.5.2, Disease Characteristics and Treatment History

Description of change: Added acceptable forms of documentation that can be used to collect prior medical history for the use of topical prescription treatments or when those treatments were not advisable.

Rationale for change: To provide guidance to the sites on the acceptable documentation for prior AD medical history.

## LIST OF ABBREVIATIONS

Abbreviation	Term
AD	atopic dermatitis
AE	adverse event
ASR	application site reaction
BID	twice daily
BSA	body surface area
CI	confidence interval
CRF	case report form
CT	continuous treatment
CTCAE	Common Terminology Criteria for Adverse Events
EASI	Eczema Area and Severity Index
EASI75	≥ 75% improvement in EASI score
eCRF	electronic case report form
EOT	end of treatment
ET	early termination
FAS	full analysis set
FDA	Food and Drug Administration
IGA	Investigator's Global Assessment
IGA-TS	Investigator's Global Assessment Treatment Success (IGA score of 0 or 1 with ≥ 2 grade improvement from baseline)
ITCH4	≥ 4-point improvement in ITCH score
LTS	long-term safety
LTS-EV	long-term safety evaluable
MedDRA	Medical Dictionary for Regulatory Activities
MPV	mean platelet volume
NCI	National Cancer Institute
NRS	numerical rating scale
PK	pharmacokinetic(s)
PT	preferred term
SAP	Statistical Analysis Plan
SOC	system organ class
TEAE	treatment-emergent adverse event
WHO	World Health Organization

## 1. INTRODUCTION

This is an open-label, 1-year safety study with an LTS period. Adolescents aged  $\geq 12$  to  $< 18$  years with AD for at least 2 years and affecting 3% to 20% BSA (excluding the scalp) plus a total IGA score of 2 or 3. The primary purpose of this study is to collect additional long-term safety data regarding the types, severity, and frequencies of TEAEs occurring in adolescents with AD who are treated with ruxolitinib 1.5% cream BID.

The purpose of this SAP is to provide details of the statistical analyses that have been outlined in the INCB 18424-315 Protocol. The scope of this plan includes the final analyses that are planned and will be executed by the Department of Biostatistics or designee and the Department of Clinical Pharmacokinetics or designee will execute the analysis of PK.

## 2. STUDY INFORMATION, OBJECTIVES, AND ENDPOINTS

### 2.1. Protocol and Case Report Form Version

This SAP is based on INCB 18424-315 Protocol Amendment 1 dated 30 NOV 2022 and CRFs approved 12 JUN 2023. Unless superseded by an amendment, this SAP will be effective for all subsequent Protocol amendments and eCRF versions.

### 2.2. Study Objectives and Endpoints

**Table 1** presents the objectives and endpoints.

**Table 1: Objectives and Endpoints**

Objectives	Endpoints
Primary	
To evaluate the long-term safety and tolerability of ruxolitinib cream in adolescents with AD.	Incidence of TEAEs, assessed by monitoring the type, frequency, and severity of AEs.
Secondary	
To further evaluate the long-term safety and tolerability of ruxolitinib cream in adolescents with AD.	Changes in vital signs, height, weight, and laboratory data for hematology and serum chemistry.
To characterize the PK of ruxolitinib cream in adolescents with AD.	Trough concentrations of ruxolitinib at each postbaseline visit.
Exploratory	

### 3. STUDY DESIGN

[figure not shown]
This is a Phase 3, open-label, 1-year safety study of ruxolitinib cream in adolescents (ages  $\geq 12$  years to  $< 18$  years) with AD whose disease is not adequately controlled with topical prescription therapies or when those therapies are not advisable.

All participants will apply ruxolitinib cream at the FDA-approved strength (1.5%) BID using the same treatment paradigm as the INCB 18424-303 and -304 Phase 3 AD studies, namely starting with an 8-week CT period during which participants will treat all baseline AD lesions, regardless of whether or not the lesion(s) improve, followed by a 44-week LTS period during which participants will only treat active AD lesions with the same treatment regimen. Participants who complete the Week 8 assessments with no safety concerns and with %BSA affected by AD no greater than 20% will continue into the LTS period.

Participants will have a safety follow-up visit 30 to 37 days following the end of treatment (Week 52/EOT2 or ET) to evaluate safety and duration of response except for participants who have been in an observation/no treatment cycle with a total IGA score of 0 from Week 48 or earlier until Week 52, for whom the Week 52/EOT2 visit will also count as the safety follow-up visit.

The study schema is presented below in [Figure 1](#).

**Figure 1: Study Design Schema**

a At Week 8, to qualify for the LTS period, an IGA score of 0 to 4 and %BSA affected by AD of 0% to  $\leq 20\%$  will be required.

b Treatment is ceased 3 days after clearing of AD lesions. Treatment is restarted if AD lesions recur. There is no limit to the number of treatment cycles during the 44-week LTS period.

#### 3.1. Randomization

Not applicable.

#### 3.2. Control of Type I Error

All statistical analyses for efficacy are exploratory in nature; therefore, no alpha control will be implemented in this study. Unless otherwise specified, all CIs provided will be at the 95% confidence level.

### **3.3. Sample Size Considerations**

The sample size is based on the evaluation of safety and is not based on statistical power calculations.

### **3.4. Schedule of Assessments**

Refer to Protocol Amendment 1 dated 30 NOV 2022 for a full description of all study procedures and assessment schedules for this study.

## **4. DATA HANDLING DEFINITIONS AND CONVENTIONS**

### **4.1. Scheduled Study Evaluations and Study Periods**

#### **4.1.1. Day 1**

Day 1 is the date that the first dose of study drug (ruxolitinib) is applied to the participants.

#### **4.1.2. Study Day**

If a visit/reporting date is on or after Day 1, then the study day at the visit/reporting date will be calculated as

$$\text{Day \#} = (\text{visit/reporting date} - \text{Day 1 date} + 1).$$

If the visit/reporting date is before Day 1, then the study day at the visit/reporting date will be calculated as

$$\text{Day \#} = (\text{visit/reporting date} - \text{Day 1 date}).$$

A study day of -1 indicates 1 day before Day 1.

#### **4.1.3. Baseline Value**

Baseline is the last nonmissing measurement obtained before the first application of ruxolitinib cream, unless otherwise defined.

When scheduled assessments and unscheduled assessments occur on the same day and the time of the assessment or time of first application is not available, use the following convention to determine baseline:

- If both a scheduled and an unscheduled visit are available on the day of the first application and the time is missing, use the scheduled assessment as baseline.
- If all scheduled assessments are missing on the day of the first application and an unscheduled assessment is available, use the unscheduled assessment as baseline.

#### **4.1.4. Handling of Missing and Incomplete Dates**

In general, values for missing dates will not be handled unless methods for handling missing dates are specified in this section or relevant sections. The following rules will be used for handling partial dates for analyses requiring dates:

- If only the day is missing, then the 15th of the month will be used.
- If both the month and day are missing, then 01 JUL of the year will be used.
- If the diagnosis date is completely missing, then the time since diagnosis will not be calculated.

### **4.2. Variable Definitions**

The following variables will only be calculated if not reported on the eCRF.

#### **4.2.1. Body Mass Index**

Body mass index will be calculated as follows:

$$\text{Body mass index (kg/m}^2\text{)} = [\text{weight (kg)}] / [\text{height (m)}]^2.$$

#### **4.2.2. Prior and Concomitant Medication**

Prior medication is defined as any nonstudy medication started before the first application of ruxolitinib cream.

Concomitant medication is defined as any nonstudy medication that is started accordingly:

- Before the date of first application of ruxolitinib cream and is ongoing throughout the study or ends on/after the date of first study drug application.
- On/after the date of first application of ruxolitinib cream and is ongoing or ends during the course of study.

A prior medication could also be classified as "both prior and concomitant medication" if the end date is on or after first application of ruxolitinib cream. In the listing, it will be indicated whether a medication is only prior, only concomitant, or both prior and concomitant.

For the purposes of analysis, all medications will be considered concomitant medications unless the medications can unequivocally be defined as not concomitant.

## **5. STATISTICAL METHODOLOGY**

### **5.1. General Methodology**

Unless otherwise noted, SAS® software (SAS Institute Inc, Cary, NC; v9 or later) will be used for the generation of all tables, graphs, and statistical analyses. Descriptive summaries for continuous variables will include but not be limited to the number of observations, mean, standard deviation, median, minimum, and maximum. Descriptive summaries for categorical variables will include the number and percentage of participants in each category.

### **5.2. Treatment Groups**

This is an open-label, single treatment group study. Participants will be summarized overall by total only.

### **5.3. Analysis Populations**

#### **5.3.1. Full Analysis Set**

The FAS will include all participants who applied ruxolitinib cream at least once.

The FAS will be used for the summary of demographics, baseline characteristics, participant disposition, analyses of all efficacy data, and safety for the CT period and for the whole study as well.

#### **5.3.2. Pharmacokinetic/Hematology Lab Evaluable Population**

The PK-evaluable population will include all participants who applied ruxolitinib cream at least once and provided at least 1 postbaseline PK sample (1 PK measurement).

The hematology lab evaluable population will include all participants who applied ruxolitinib cream at least once, provided the baseline hematology blood sample, and at least 1 postbaseline hematology blood sample (1 hematology measurement).

The PK/hematology lab evaluable population will include all participants who are both PK evaluable and hematology lab evaluable.

#### **5.3.3. Long-Term Safety Evaluable Population**

All participants who applied ruxolitinib cream at least once during the LTS period will constitute the LTS-EV population. All safety analyses for the LTS period will be conducted with the LTS-EV population.

## 6. BASELINE, EXPOSURE, AND DISPOSITION

[Appendix A](#) provides a list of data displays. Sample data displays are included in a separate document.

### 6.1. Demographics, Baseline Characteristics, and Disease History

#### 6.1.1. Demographics and Baseline Characteristics

The following demographics and baseline characteristics will be summarized for the FAS: age, sex, race, ethnicity, weight, height, and BMI.

#### 6.1.2. Baseline Disease Characteristics

The following baseline disease characteristics will be summarized for the FAS:

- Baseline IGA score (2 or 3)
- Baseline facial IGA score
- Baseline EASI score
- Baseline Itch NRS (by-visit, daily)
- Time (years) since first onset of AD
- Prior history of asthma (no/yes)
- Prior allergies (food, environmental; no/yes)
- History of contact dermatitis (no/yes)
- Common complications of AD
- Time since onset of current AD episode
- Number of AD episodes/flare over the last 12 months
- Prior therapy for AD given in the past 12 months (no/yes)
- Total %BSA involvement in current AD episode
- Facial and/or neck involvement during past episodes/flares (no/yes)
- Average duration of episodes/flares

#### 6.1.3. Prior Therapy for Atopic Dermatitis

Prior therapies for AD, including medication and other types of therapies, during the past 12 months will be coded using the WHO Drug Dictionary and summarized. The type of treatment and reason for discontinuation will be summarized as well.

#### 6.1.4. Medical History

For participants in the FAS, medical history will be summarized. This summation will include the number and percentage of participants with medical history event for each body system/organ class as documented on the eCRF.

## **6.2. Disposition of Participant**

The number and percentage of participants who were treated, who completed CT period, who discontinued study treatment, or who withdraw from the study during the CT period with a primary reason for discontinuation will be summarized and listed for the FAS population during the CT period.

The number and percentage of participants who were treated, who completed LTS period, who discontinued study treatment, or who withdraw from the study during the LTS period with a primary reason for discontinuation will be summarized and listed for the LTS-EV population during the LTS period.

## **6.3. Protocol Deviations**

Protocol deviations will be summarized and listed for the CT and LTS periods separately.

## **6.4. Exposure**

For participants in the FAS and LTS-EV populations, descriptive statistics will be provided for duration of treatment (ie, the average daily amount of cream applied [g], and the total amount of cream applied [g]), respectively. Duration of treatment with ruxolitinib cream is defined as the number of days from Day 1 to the date of last record of ruxolitinib cream application.

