### Tables

Table No.	Title	Population
Baseline and Demographics Characteristics		
1.1 Disposition		
1.1.1	Analysis Populations	FAS
1.1.2.1	Summary of Participant Disposition in the CT Period	FAS
1.1.2.2	Summary of Participant Disposition in the LTS Period	LTS-EV
1.1.3	Summary of Number of Participants Enrolled by Country and Site	FAS
1.1.4.1	Summary of Protocol Deviations for the CT Period	FAS
1.1.4.2	Summary of Protocol Deviations for the LTS Period	LTS-EV
1.2 Demography and Baseline Characteristics		
1.2	Summary of Demographics and Baseline Characteristics	FAS
1.3 Baseline Disease Characteristics		
1.3	Summary of Baseline Disease Characteristics	FAS
1.4 Prior Medication and Concomitant Medication		
1.4.1	Summary of Prior Medications	FAS
1.4.2	Summary of Prior Medications for Atopic Dermatitis	FAS
1.4.3.1	Summary of Concomitant Medications in the CT Period	FAS
1.4.3.2	Summary of Concomitant Medications in the LTS Period	LTS-EV
1.5+ Others		
1.5	Summary of General Medical History	FAS
Efficacy		
2.1 IGA		
2.1.1.1	Summary of Participants Achieving IGA-TS by Visit	FAS
2.1.1.2	Summary of Participants in Each Category of IGA Score by Visit	FAS
2.1.1.3	Summary of Participants Achieving an IGA score of 0 or 1 by Visit	FAS
2.1.1.4	Summary of Participants Achieving a Facial IGA score of 0 or 1 by Visit	FAS
2.2 EASI		
2.2.1	Summary of Participants Achieving EASI75 by Visit During the Treatment Period	FAS
2.2.2	Summary of EASI Score by Visit During the Treatment Period	FAS
2.3 Itch NRS Score		
2.3.1	Summary of Participants Achieving $\geq$ 4-Point Improvement in Itch NRS Score by Visit During the Treatment Period	FAS with baseline Itch NRS score $\geq$ 4
2.3.2	Summary of By-Visit Itch NRS Score	FAS
2.3.3	Summary of Participant Achieving $\geq$ 4-Point Improvement in Daily Itch NRS Score	FAS with baseline Itch NRS score $\geq$ 4
2.3.4	Summary of Daily Itch NRS Score	FAS

Table No.	Title	Population
2.4 BSA		
2.4.1	Summary and Analysis of Total %BSA Affected by AD	FAS
Safety		
3.1 Exposure		
3.1.1.1	Summary of Exposure in the CT Period	FAS
3.1.1.2	Summary of Exposure in the LTS Period	LTS-EV
3.1.1.3	Summary of Exposure from Baseline to Week 52	FAS
3.1.2	Summary of Study Drug Compliance in the CT Period	FAS
3.1.3	Summary of Study Drug Compliance in the LTS Period	LTS-EV
3.2 Adverse Events		
3.2.1.1.1	Overall Summary of Treatment-Emergent Adverse Events in the CT Period	FAS

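### SAP 6.4 counts duration of treatment from Day 1 for the LTS-EV population as well, so the LTS exposure table as written includes the eight-week CT period; time on treatment is not measured

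*SAP*

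**What the plan says.** SAP 6.4 (Exposure) covers the FAS and the LTS-EV population in one sentence, promising descriptive statistics for "duration of treatment (ie, the average daily amount of cream applied [g], and the total amount of cream applied [g"]). It then gives a single definition: duration of treatment "is defined as the number of days from Day 1 to the date of last record of ruxolitinib cream application".

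SAP 4.1.1 fixes the starting point: "Day 1 is the date that the first dose of study drug (ruxolitinib) is applied to the participants". The SAP defines no separate first day for the LTS period.

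SAP Appendix A plans three exposure tables: 3.1.1.1, "Summary of Exposure in the CT Period" (FAS); 3.1.1.2, "Summary of Exposure in the LTS Period" (LTS-EV); and 3.1.1.3, "Summary of Exposure from Baseline to Week 52" (FAS). The population for the second is defined in SAP 5.3.3: "All participants who applied ruxolitinib cream at least once during the LTS period will constitute the LTS-EV population".

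Treatment is continuous for the first 8 weeks. In the 44-week LTS period it stops after lesions clear and restarts on recurrence, with no limit on the number of cycles (SAP Figure 1, footnote b; Protocol 6.1). Cycle start and end dates are recorded at LTS visits (Protocol Table 4), and participants log daily applications in an eDiary (Protocol 6.1.1).

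**The concern.** One start date cannot serve all three tables. Day 1 is right for the CT table and the whole-study table. For the LTS table it is wrong: every LTS-EV participant began treatment in the CT period, so a count from Day 1 adds those weeks to a figure labelled as LTS exposure. SAP 6.2 and 6.3 say explicitly which period their summaries cover; 6.4 does not.

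Two further gaps lie in the same section. First, a span from first to last application includes the drug-free stretches between LTS cycles, and 6.4 offers nothing that shows how long participants were actually being treated. In a one-year safety study of an intermittently used product, that is basic context for reading the adverse event tables. Second, the parenthesis in 6.4 equates duration with two amounts in grams, and average daily grams has no stated denominator.

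**Working it through.** The SAP reports no exposure figure to reproduce, so the check is day arithmetic on its own definition.

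**Inputs**
- CT period 8 weeks = 8 × 7 = 56 days; LTS period 44 weeks = 44 × 7 = 308 days; total 364 days (Protocol 4.2).
- The LTS period starts at the Week 8 visit (Protocol 4.1), nominally Day 57. The window of ±3 days (Protocol Table 3) gives Day 54 to Day 60.
- The last possible application is the evening before the Week 52 visit (Protocol 6.1), nominally Day 364.

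**Formulas, both end dates counted.** Let L be the study day of the last application and f the study day of the first LTS application.
- As written: L − 1 + 1 = L.
- Bounded to the LTS period: L − f + 1.
- Excess: f − 1. This does not depend on L, and it is the same if only one end date is counted.

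**Excess in the LTS table**
- Cream applied from the Week 8 visit on: 57 − 1 = 56 days; across the window, 54 − 1 = 53 to 60 − 1 = 59 days.
- A participant who is clear at Week 8 and resumes later has a larger excess. With a first LTS application on Day 141 it is 140 days.

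**Effect by last application (f = 57)**

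| Last application | As written | LTS-bounded | Ratio |
|---|---|---|---|
| Day 364 | 364 | 364 − 56 = 308 | 1.18 |
| Day 140 | 140 | 140 − 56 = 84 | 1.67 |

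The relative error is largest for those who stop early.

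**Elapsed time against time on treatment (a separate matter).** Take an illustrative participant treated on Days 1–56, 141–196 and 309–364.
- LTS table as written: 364 days.
- LTS-bounded elapsed time: 364 − 141 + 1 = 224 days.
- LTS days on treatment: 56 + 56 = 112.
- Whole study: 364 days elapsed, 56 + 112 = 168 days on treatment.

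The documents give no treated share of LTS days. If it were 75%, 50% or 25% of 308 days, days on treatment would be 231, 154 or 77, while LTS elapsed time could lie anywhere between that number and 308. These figures show how far two different measures can diverge. They are not the size of an error.

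**Average daily grams.** If LTS grams were divided by the Day 1-based duration, a participant treated up to Day 364 would show 308/364 = 0.846 of the average based on LTS elapsed days. This is conditional, because 6.4 does not say what the divisor is.

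**The case against.** The strongest reply is that the intent is plain. Table 3.1.1.2 is titled for the LTS period, its population is defined by LTS applications, and SAP section 6 notes: "Sample data displays are included in a separate document". Appendix A also refers to a set of standard safety table conventions. Either document may already set period limits. This stands as far as it goes: the text does not prove that the table will be programmed wrongly. But the only derivation rule in the SAP conflicts with the title, and a title does not replace a rule.

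A reader might go further and infer that the CT table is also wrong, showing 364 days instead of 56 for a participant treated to the end. The documents do not support that. In a table limited to the CT period, the last record is naturally the last CT record, and Day 1 is already the right start. The larger figure appears only if LTS applications are fed into a table whose title excludes them. One clarifying phrase is enough.

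A reader might also infer that elapsed duration is itself an error because treatment is intermittent. It is not. Day 1 to last application is a valid elapsed measure for the whole study, and total grams partly conveys the amount used. SAP 6.5 also uses days in treatment, less approved interruptions, as a compliance denominator, though that is not an exposure summary. A time-on-treatment measure is a worthwhile addition, not the correction of a wrong number.

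The wording of the parenthesis is a drafting slip and no more.

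**Conclusion.** The point holds for one table. Followed as written, SAP 6.4 makes LTS duration in Table 3.1.1.2 too long by about 56 days (53 to 59 with the visit window, more when LTS treatment starts later). That is 18% too long for a participant treated from the Week 8 visit to Day 364 and 67% too long for one whose last application is on Day 140. This assumes nominal visit timing and that no unseen shell or convention overrides the text. Confidence is high that the wording is deficient; whether the produced table would be wrong cannot be judged from these documents.

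The missing time-on-treatment measure and the undefined daily-average denominator are gaps worth closing. No endpoint, no planned TEAE number or percentage, and no whole-study total of grams changes. Severity is minor.

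**What to change.** Amend SAP 6.4 as follows.

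- **Start and end per table, both dates counted.** CT: Day 1 to the last application before LTS entry, or to the last application if treatment ended in the CT period, with or without an ET visit. LTS: first to last application in the LTS period. Whole study: Day 1 to the last application. If a dose before the visit and a clinic dose fall on the same Week 8 date, that date may count in both period tables but only once in the whole-study total.
- **Days on treatment, separately labelled.** LTS: the sum of days within recorded treatment cycles, clipped to the LTS period. Use eDiary records to check or fill missing cycle dates, and leave out a cycle-end visit date on which no cream was applied. Missed doses within a cycle stay in the count and are handled as compliance; otherwise average daily grams would rise as doses are skipped. CT: elapsed CT duration less recorded full interruptions. Withholding at a single lesional site, which Protocol 6.5.1 records as a dose interruption, does not count as one for this purpose. Align the variable with days in treatment in SAP 6.5.
- **Three measures.** List duration in days, average daily grams and total grams separately, and state that average daily grams is total grams in the period divided by days on treatment in that period.

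The cost is SAP wording and a few derived variables, with no new data collection and no change to the adverse event summaries. The downside is that cycle dates are recorded by participants and some may be missing, so the SAP should report how many were filled from the eDiary.
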